2.1 Adverse event (AE)

Adverse events are defined as any undesirable experience occurring to a subject during a clinical trial, whether or not considered related to the investigational treatment. All adverse events reported spontaneously by the subject observed by the investigator or her staff will be recorded.

2.2 Serious adverse event (SAE)

A serious adverse event is any untoward medical occurrence or effect that:

- results in death; or
- requires hospitalization or prolongation of existing inpatients' hospitalization; or
- results in persistent or significant disability or incapacity; or
- is a new event of the trial likely to affect the safety of the subject, such as an unexpected outcome of an adverse reaction.

All SAE's will be reported to the accredited Ethical Committee that approved the protocol.

2.3 Suspected unexpected serious adverse reactions (SUSAR)

Not applicable.

3. Follow-up of adverse events

AE according to the study are considered very unlikely, due to the fact that only non-invasive methods are used. All AEs will be followed until a stable situation has been reached and treated to standard procedures.

4. Data Safety Monitoring Board (DSMB)

Not applicable.

STATISTICAL ANALYSIS

A table with baseline characteristics of all subjects will be provided. Baseline characteristics of the population will be expressed as the mean \pm standard deviation if normally distributed, or as the median [25th – 75th percentile] as not normally distributed, for continuous and dichotomous data, and as the frequency (%) for categorical data. Measurements of drop-outs will be included until the moment of withdrawal from the study. Normality in distribution will be tested by the Shapiro-Wilk statistic. Repeated measurements ANOVA techniques will be used for analysis. Pearson's Chi-squared test will be used to assess whether there is any distinction between subgroups in rate of kidney function decline. In case the analysis of the baseline characteristics showed any clinically relevant imbalance, we will also perform a multivariable logistic regression analysis in order to correct for this imbalance. Differences in LVH will be corrected for systolic BP and haemoglobin, as these are predictors of LVH in predialysis population.¹⁵ Depending on the level of measurement a Chi-squared test or a T-test will be used to assess differences in secondary study parameters, and logistic and linear regression for baseline-corrected estimates. Tests will be considered significant if p-values are ≤ 0.05 .

ETHICAL CONSIDERATIONS

1. Regulation statement

The study will be conducted according to the principles of the Declaration of Helsinki (Fortaleza, Brasil, 2013).

2. Recruitment and consent

All eligible patients and/or their legal representatives will receive an information leaflet by the researcher. The leaflet informs about the aims and conduct of the study, the burden and risks associated with participation. If the patient is interested in participation, he or she will mention his or her interest to the researcher, who will explain the procedure verbally in detail. Each participant will have at least one week time to decide whether he or she wishes to participate in the study. The consent and insurance procedures will be explained by the researcher. After signing the informed consent form, the study will be initiated.

3. Objection by minors or incapacitated subjects

Not applicable.

4. Benefits and risks assessment, group relatedness

Only non-invasive techniques which pose a minimal burden to the patient will be used. Blood sampling will coincide as much as possible with regular blood takings for clinical purposes. The risk of venipuncture-related complications is considered low. The burden associated with BIS and BP measurements is considered low. All subjects undergo echocardiography. Costs of this examination

will not be charged to the patient. Analysis of the echocardiography will be done during follow-up period. Aberrant results will be discussed with an expert.

5. Compensation for injury

In case of injury due participation to HORUZ study, the sponsor has a liability insurance which is in accordance with the legal requirements in Belgium: 'de wet inzake experimenten op de menselijke person van 7 mei 2004'. This insurance provides cover for damage to research subjects through injury or death caused by the study.

6. Incentives

No direct incentives will be given to the participants. None of the research examinations will be charged to the patients. For each study visit, parking ticket will be provided.

ADMINISTRATIVE ASPECTS AND PUBLICATION

1. Handling and storage of data and documents

All documents will be handled confidentially according to the General Data Protection Regulation. Storage of all data occurs on the 'T-schijf' of Ziekenhuis Oost-Limburg Genk.

2. Amendments

All amendments will be notified to the Ethical Committee that gave a favorable opinion.

3. Annual progress report

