- Clinical conditions affecting body composition: liver cirrhosis, active infectious disease or any acute CV event (defined as cerebrovascular event, myocard infarction, decompensatio cordis) during the 3 months before screening for inclusion
- Pregnancy

- Not able to sign informed consent

4. Sample size calculation

The primary outcome parameter is the mean eGFR decline which will be compared between the FOgroup and the non-FO-group. We hypothesize that the mean difference between eGFR between these two groups will be 2 μ mol/ml/year. Because the study of Levin et al. does not report a SD, we take the SD of the MDRD study¹: 4.7 μ mol/ml/year^{1,42,43}. In order to show an alpha of 0.05 and a power of 0.8, at least 86 patients would be needed per group. In order to correct for drop-outs, at least 103 patients per group have to be included.

METHODS

1. Study parameters/endpoints

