1.1 Demographic and clinical data

The prevalent CKD stage 3 – 5 population will be screened by the researcher. After verification of the in- and exclusion criteria, eligible patients will be invited to participate the HORUZ study, with approval of their treating nephrologist. After signing the informed consent, data at baseline and during followup visits will be collected on paper clinical report forms (Table 1). Hypertension is defined as an office BP \geq 140/90 mmHg or home BP \geq 130/80 mmHg, or current medication for hypertension.¹ Diabetes mellitus will be assumed to be present in patients who report use of insulin and/or oral hypoglycemic agents. CV diseases include coronary artery disease, as documented by coronary angiography or a history of myocardial infarction, congestive heart failure, cerebrovascular accident, or known peripheral vascular disease. Fluid assessments, including BIS measurements, will be recorded on the HORUZ registration form (Appendix).

The healthy controls included for the cross-sectional analysis will only be followed according to visit 0 and 1.

| | Baseline Visit 0 | Month 1 Visit 1 | Month 3 Visit 2 | Month 6 Visit 3 | Month 9 Visit 4 | Month 12/ end of study Visit 5 |
|--|---------------------|--------------------|--------------------|--------------------|--------------------|-----------------------------------|
| Consent | х | | | | | |
| Demographics: Age (y) Gender Height (cm) Smoking status Etiology CKD Hypertension Diabetes CV disease Tx list | x | | | | | |
| eGFR _{creat} | x | x | x | x | x | x |
| CrUrCl | | x | x | x | x | x |
| 24h urine | | x | x | x | x | x |

Table 1 Schedule of the main data to collect in CKD subjects.

| BP | x | | x | x | x | x |
|-----------------|---|---|---|---|---|---|
| ECG | x | | x | x | x | x |
| Echo cor | | x | | | | x |
| CV events | | x | x | x | x | x |
| Hospitalization | | x | x | x | x | x |
| Medication | x | | x | x | x | x |
| Whole body BIS | x | | x | x | x | x |
| Thoracic BIS | x | | x | x | x | x |
| SF36 | x | | | | | x |
| Adverse event | | x | x | x | x | x |

Abbreviations: BIS, bioimpedance spectroscopy; BP, blood pressure; CKD, chronic kidney failure; Creat, creatinine; CrUrCl, mixed creatinine

and urea clearance; CV, cardiovascular; ECG, electrocardiography; M, month; SF36, short form 36 questionnaire; Tx, transplantation.

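### Yes/no baseline variables are assigned to mean or median with quartiles, a summary that cannot show a proportion and could hide an imbalance between the fluid-overload groups in the printed table

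*Combined protocol and SAP*

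**What the plan says.** The relevant rules are all in the opening paragraph of the Statistical Analysis section.

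- The table: "A table with baseline characteristics of all subjects will be provided". No split by fluid status is stated.
- The summaries: mean ± SD if normal, otherwise median with 25th and 75th percentiles, "for continuous and dichotomous data, and as the frequency (%) for categorical data".
- The switch between mean and median: "Normality in distribution will be tested by the Shapiro-Wilk statistic".
- The condition for adjustment: "In case the analysis of the baseline characteristics showed any clinically relevant imbalance, we will also perform a multivariable logistic regression analysis". This sentence names no test, threshold or summary statistic.

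Table 1 (Methods 1.1) lists the baseline items as age and "Gender Height (cm) Smoking status Etiology CKD Hypertension Diabetes CV disease Tx list". The registration form in the Appendix records hypertension, diabetes, CV disease and transplant-list status as no/yes and gender as M/F. Diabetes, for example, is present or absent by reported drug use: "Diabetes mellitus will be assumed to be present in patients who report use of insulin and/or oral hypoglycemic agents".

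**The concern.** The sentence on summaries names dichotomous data explicitly and places them with continuous data. Frequency (%) is left for a separate class. A median with quartiles of a 0/1 variable says only which quarter of the range the proportion falls in. Two groups can differ by more than 20 percentage points and print the same, and two nearly equal groups can print differently.

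This matters more here than in a randomised trial. The FO and non-FO groups are formed by a measurement at baseline, and the Introduction itself describes fluid overload as both a cause and a consequence of renocardiac complications. Differences in comorbidity between the groups are therefore plausible. The baseline table is where a reader would look for them and where the decision to adjust would be checked.

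**Working it through.** **Group size.** Study Population, section 4 (Sample size calculation) gives a difference of 2 per year, an SD of 4.7 per year, alpha 0.05 and power 0.8.

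n per group = 2 × [4.7 × (1.96 + 0.84) / 2]² = 86.6

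The plan states 86. Rounding up gives 87, and power at 86 is 79.7%, so the figure is reproduced closely enough. The plan enrols 103 per group, which corresponds to 86 / (1 − 0.165). These figures serve here only as group sizes.

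**Which branch of the rule applies.** Shapiro-Wilk was run on 0/1 vectors of 86 and of 103 values, with prevalences from 24% to 76%. The largest p-value was 2.8 × 10⁻¹³. Normality is rejected every time, so only the median branch can be reached.

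**What the median branch prints at n = 103.** Order the values as 103 − k zeros followed by k ones.

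- The median is the 52nd value. It is 0 if k ≤ 51 and 1 if k ≥ 52.
- The 75th percentile lies between the 77th and 78th values (linear interpolation). It is 0 if k ≤ 25 and 1 if k ≥ 27. At k = 26 it is 0.5, 0.75 or 1, depending on the percentile definition.
- By symmetry, the 25th percentile is 0 if k ≤ 76 and 1 if k ≥ 78.

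Apart from values on the boundaries, only four results are possible: 0 [0–0] below about 25%, 0 [0–1] from 25% to 50%, 1 [0–1] from 50% to 75%, and 1 [1–1] above that.

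**Illustration.** The documents give no prevalences by group, so the counts below are assumptions.

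| Group A | Group B | Printed as planned | Printed as n (%) |
|---|---|---|---|
| 27/103 | 50/103 | 0 [0–1] and 0 [0–1] | 27 (26.2%) and 50 (48.5%) |
| 25/103 | 27/103 | 0 [0–0] and 0 [0–1] | 25 (24.3%) and 27 (26.2%) |

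For the first row:

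- Difference = 23/103 = 0.223.
- Standardised difference = 0.223 / √[(0.262 × 0.738 + 0.485 × 0.515) / 2] = 0.47.
- Pooled proportion = 77/206 = 0.374. Pearson chi-squared = 0.2233² / (0.3738 × 0.6262 × 2/103) = 10.97, p = 0.0009.

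The second row differs by 2/103, or 1.9 percentage points, yet it is the row in which the printed summaries differ.

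**At n = 86.** 42/86 prints 0 [0–1]. 22/86 has a 75th percentile of 0.75 or 1, depending on the definition, and from 23/86 it is 1 under all three definitions tried. As n (%), 22 (25.6%) against 42 (48.8%) has a standardised difference of 0.50 and p = 0.0016.

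**What the raw data show.** At n = 103 the first row gives p = 0.0009 by chi-squared, 0.0010 by Mann-Whitney and 0.0008 by t-test. The information is lost in the printed summary, not in the data.

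**The case against.** The best defence is that this is a drafting slip. Dichotomous data are a kind of categorical data, the same sentence gives frequency (%) for categorical data, and the secondary analyses choose between a chi-squared test and a t-test by level of measurement. The authors probably intended n (%). That may be so, but the text names dichotomous data and assigns them elsewhere, nothing in the document corrects it, and a table program written from the plan could follow it.

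A reader might go further and infer that the imbalance check itself is blind to such differences. The documents do not support this. The condition for adjustment refers to an analysis of the baseline characteristics and is not tied to printed medians. Any comparison of the underlying 0/1 data would show the difference.

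A reader might also infer that the display biases the primary comparison by some amount. That does not follow either. It would need prevalences and covariate effects that the documents do not give. The adjustment named is also a logistic regression, whereas the primary endpoint is a continuous eGFR slope, so even a perfect imbalance check would not, as written, give an adjusted difference in mean slope.

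Two further points stand. The 26% and 49% lie near the two edges of one band, so they show close to the most that can be hidden; a gap that crosses 25%, 50% or 75% would print differently. And because no split by FO group is stated, changing to n (%) without splitting the table would not reveal an imbalance.

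**Conclusion.** The point holds as a defect of descriptive reporting. On the plan's own rules, yes/no baseline variables are reduced to medians with quartiles, which cannot show a proportion. Within a band such as 25% to 50%, a difference of about 22 percentage points disappears from print; across a band edge, a 2-point difference looks like a change.

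Since the groups are not randomised and the plan specifies no other display or test of baseline imbalance, a reader could not verify from the table whether the decision to adjust was sound. An analyst with the raw data could still judge it.

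The Shapiro-Wilk and quartile results follow from the rule and the planned group sizes. The example prevalences and the equal split of 103 and 103 are assumptions. No test, effect estimate or sample size is affected, and no bias in the primary result can be attributed to this wording.

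**What to change.** Reword the sentence along these lines: *mean ± SD or median [25th–75th percentile] for continuous data, and number (%) for dichotomous and categorical data*.

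State that the baseline table is shown by FO and non-FO group, and that imbalance in yes/no variables is judged on the difference in percentages.

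The cost is a sentence or two in the Statistical Analysis section and a table layout, notified to the ethics committee like any other amendment. It needs no new data, visits or patients.

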1.2 Primary endpoint

The association between fluid status and kidney function decline in patients with CKD stage 3 (CKD-EPI 60-30ml/min), 4 (CKD-EPI 30-15ml/min) and 5 (CKD-EPI < 15 ml/min) is the primary objective of the HORUZ study.

The primary endpoint is the mean eGFR decline which will be compared between the FO-group and the non-FO-group. BIS-measured FO will be expressed as overhydration (OH) normalized to ECW and noted as a percentage of ECW (OH/ECW).^{6,44} FO is defined as an OH/ECW \geq 7% (or an absolute OH \geq 1.1 L).⁴⁵

Rate of kidney function decline will be assessed by the slope in eGFR_{creat} CKD-EPI (see formula below), defined as the regression coefficient between eGFR_{creat} and time, in units of mL/min/1.73m² per year. At least 3 eGFR_{creat} values are required to evaluate eGFR_{creat} slope. All eGFR_{creat} CKD-EPI will be uniformly calculated in the laboratory. eGFR_{creat} decline is assessed by changes in eGFR over time. Rapid eGFR_{creat} decline is defined as the quartile with the steepest eGFR slope (eGFR_{creat} decline > $3mL/min/1.73m^2$ per year).⁹

Investigating the Hemodynamic profile Of chronic Renal patients by Use of Bioimpedance HORUZ study

 $eGFR_{creat} = 141 \times min(S_{creat}/\kappa, 1)^{\alpha} \times max(S_{creat}/\kappa, 1)^{-1.209} \times 0.993^{Age} \times 1.018$ [if female] × 1.159 [if black]

 $\begin{array}{l} S_{creat} \left(standardized \ serum \ creatinine \right) = mg/dL \\ \kappa = 0.7 \ (females) \ or \ 0.9 \ (males) \\ \alpha = -0.329 \ (females) \ or \ -0.411 \ (males) \\ min = indicates \ the \ minimum \ of \ S_{creat}/\kappa \ or \ 1 \\ max = indicates \ the \ maximum \ of \ S_{creat}/\kappa \ or \ 1 \\ age = years \end{array}$

Average CrUrCl will be determined by creatinine and urea measurements in blood- and urine samples (Table 2).

Residual urine output (mL per 24h) will be collected every study visit and analyzed on volume, urea, creatinine, sodium, osmolarity and albumin/creatinine ratio (ACR) (Table 2).

Time to renal replacement therapy will be recorded.

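### The Statistical Analysis section does not state the FO versus non-FO comparison of eGFR slope, and its logistic correction for imbalance cannot adjust that slope

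*Combined protocol and SAP*

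**What the plan says.** Methods 1.2 (Primary endpoint) fixes the quantity: "The primary endpoint is the mean eGFR decline which will be compared between the FO-group and the non-FO-group". Decline is the regression coefficient of eGFR on time for each patient, in mL/min/1.73m² per year, and "At least 3 eGFR_{creat} values are required to evaluate eGFR_{creat} slope". The same section also defines a binary version: rapid decline "is defined as the quartile with the steepest eGFR slope", glossed as a loss of more than 3 per year.

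Study Population 4 (Sample size calculation) assumes a mean difference of 2 and an SD of 4.7, giving 86 per group, or 103 with drop-outs.

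The Statistical Analysis section contains four relevant statements:

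- A general one: "Repeated measurements ANOVA techniques will be used for analysis".
- One on decline: "Pearson's Chi-squared test will be used to assess whether there is any distinction between subgroups in rate of kidney function decline".
- One on imbalance, which applies if a clinically relevant baseline imbalance is seen: "we will also perform a multivariable logistic regression analysis in order to correct for this imbalance".
- One on other outcomes: "a Chi-squared test or a T-test will be used to assess differences in secondary study parameters, and logistic and linear regression for baseline-corrected estimates".

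The Summary and Study Design describe the study as non-randomised, and Methods 2 gives randomisation as not applicable.

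**The concern.** The endpoint and the sample size both describe a difference between two mean slopes. The analysis section never states that contrast. The repeated-measures sentence does not say what is analysed, between which groups, or which term carries the result. The chi-squared sentence speaks of unspecified subgroups and fits the rapid-decline category, not a mean.

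The imbalance rule matters more. FO and non-FO patients can be expected to differ in other ways that affect kidney function, so the primary conclusion depends on adjustment. Logistic regression needs a binary outcome. Applied to rapid decline, it gives an odds ratio on a cut slope; it does not give an adjusted difference in mL/min/1.73m² per year. An analyst who follows the text literally must choose between an unadjusted slope difference, an adjusted odds ratio for a different endpoint, and an ANOVA contrast that the plan does not define. These can disagree, and nothing in the plan says which one decides.

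**Working it through.** **Inputs.** Difference 2, SD 4.7, alpha 0.05, power 0.80 and 86 per group come from the sample size section. The printed unit there is not a slope unit; I read both figures as mL/min/1.73m² per year. Assumed: two-sided test, equal groups, normally distributed slopes.

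**1. Which analysis the sample size belongs to.** n per group = 2 × [4.7 × (1.960 + 0.842) / 2]² = 86.7, against the stated 86. A one-sided test would need 69. So the plan is sized for a two-sided comparison of two means. The standard error at 86 per group is 4.7 × √(2/86) = 0.717, and power by the noncentral t distribution is 79%.

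**2. Power if chi-squared were the deciding test.**

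- *Steepest quartile.* The standardised difference is 2/4.7 = 0.426. The cut that puts 25% of all patients above it gives 18.3% rapid decliners in non-FO and 31.7% in FO. Simulated power is 46-47%. The usual formula gives 52%. The gap arises because exactly 43 of 172 patients fall in the quartile, which makes the test conservative (true size about 3%).
- *Cut at more than 3 per year.* This needs an assumed mean decline in non-FO:

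| Non-FO mean decline | Non-FO above cut | FO above cut |
|---|---|---|
| 1 | 33.5% | 50.0% |
| 2 | 41.6% | 58.4% |
| 3 | 50.0% | 66.5% |
| 4 | 58.4% | 73.8% |

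Simulated power is about 60-63% for means of 1 to 3 and about 57% at 4.

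**3. What adjustment does.** Assume one covariate that is 0.5 SD higher in FO and steepens decline by g = 1 (in brackets: g = 2) per SD, with within-group slope SD still 4.7.

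- *Unadjusted.* The shift is 0.5 × g = 0.5 (1.0), so a true difference of 2 is estimated as 2.5 (3.0). With no true difference, the test statistic is centred at 0.5/0.717 = 0.70 (1.0/0.717 = 1.40), and a significant result appears in about 10-11% (28-29%) of trials instead of 5%.
- *Linear adjustment.* The estimate returns to 2.0 and false positives to about 5%. The standard error is √(4.7² − g²) × √(2/86) × √(1 + 0.5²/4) = 0.722 (0.669), giving power of about 78-79% (85%).
- *Logistic adjustment.* Simulated power is about 50% (55%) on the quartile and 59% (63%) on the cut at 3, with no estimate in slope units.

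**4. Form of adjustment in a mixed model.** A covariate main effect shifts a patient's eGFR level, not the slope. In simulation (six visits, residual SD 2.5 assumed, no true difference), adding only the main effect left the FO-by-time bias at about 0.5 (1.0), with 11% (29%) significant. Adding covariate-by-time brought it to about zero and 5%.

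**The case against.** **The plan does name a model class.** With eGFR scheduled at six visits and two groups compared on decline, repeated-measures ANOVA can naturally be read as a group-by-time test. That stands: a reader who infers that the plan has no analysis at all for the primary endpoint goes too far. What is missing is the contrast and its link to the per-patient slope. That reading also leaves the adjustment unresolved.

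**Linear regression is named.** It is, for baseline-corrected estimates, but inside the sentence on secondary parameters. Whether it reaches the primary endpoint is unclear, so it does not settle the matter.

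**Adjustment is promised.** True. The shifted differences and raised false-positive rates in step 3 arise only if no adjustment is made; they are not a prediction of what the plan will produce. They show why an adjusted slope estimate is needed. The covariate shift and effects are assumed, and the documents give neither. Nor has it been shown that logistic adjustment would leave confounding in its own binary outcome; the objection to it is that the outcome is a different one.

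**Two other inferences fail.** A reader might see a conflict between ANOVA and the sentence "Measurements of drop-outs will be included until the moment of withdrawal from the study", because classical software drops incomplete cases. The plan never specifies complete cases, so the text does not support that conflict. A reader might also fault unweighted slopes from patients with few visits. Such a comparison remains valid when loss is random, so this is a question of precision and not an error in the plan.

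**Conclusion.** The point holds as a defect in the stated rules: followed literally, the Statistical Analysis section yields no adjusted difference in mean eGFR slope, although that is what the primary endpoint of a non-randomised comparison calls for. The conclusion rests on comparing the sections with one another and needs none of the simulated figures.

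The figures indicate scale under the assumptions above. Letting chi-squared decide would reduce power from 79% to about 46-47% or 57-63%, depending on the cut. Omitting adjustment for a moderate confounder would add 0.5 to 1.0 to a planned difference of 2. The text does not support the stronger claim that the trial will have such low power or such bias, because it does not make chi-squared the deciding test and does promise some adjustment.

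The estimand and the sample size are not in question. It should be corrected before analysis because confounding control carries the primary result.

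**What to change.** In the Statistical Analysis section:

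1. State that the primary analysis is the FO versus non-FO difference in eGFR slope, in mL/min/1.73m² per year, with its 95% CI. Use either a linear regression of the per-patient slopes on FO group and baseline covariates, or a linear mixed model of all eGFR values in which the FO-by-time coefficient is the result. Either closes the gap; choose one in advance.
2. For the primary endpoint, replace the logistic correction with this linear adjustment and list the covariates. In a mixed model, include covariate-by-time terms, since main effects alone leave the slope difference confounded. Say whether the three-value rule still applies.
3. Label the chi-squared and logistic analyses as secondary analyses of rapid decline.

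The cost is a few sentences and a little more analysis work, with no change in patients or visits. One limit remains: a mixed model does not remove bias if leaving the study depends on a patient's true slope.

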IVS = interventricular septum thickness PWT = posterior wall thickness EDD = end diastolic diameter of the left ventricle

LVEF will be calculated using diastolic and systolic LV volumes measured by the single-plane Simpson's

rule method: ((Dvol - Svol)/Dvol) x 100; 0.50 is the cutoff point.

LV geometry is divided into four categories, based on LVMI and RWT:

[figure not shown]

Figure 5 Left ventricle classification system of Koren et al., adapted from Middleton et al.¹⁷

Diastolic dysfunction is defined as an abnormality of diastolic distensibility, filling, or relaxation of the left ventricle, regardless of whether the ejection fraction is normal or abnormal and whether the patient is symptomatic or asymptomatic.⁴⁶

4. Withdrawal of individual subjects

Participants can exit the study at any time for any reason if they wish to do so. The investigator can decide to withdraw a subject from the study for urgent medical reasons. In case of withdrawal, an end of study visit will be scheduled to perform last measurements according to visit 5. As there is no medication intervention in this study, there is no need for a safety procedure during withdrawal. Withdrawals will not be further followed.

5. Replacement of subjects withdrawn from treatment

Patients who withdraw from the study will not be replaced, as this has already been taken into account in the sample size calculation.

6. Premature termination of the study

As the interventions in this study are non-invasive and no medication is used, no specific termination criteria are formulated.

SAFETY REPORTING

1. Temporary halt for reasons of subject safety

The sponsor will suspend the study if there is sufficient ground that continuation of the study will jeopardize subject health or safety. The sponsor will notify the accredited Ethical Committee without undue delay of a temporary halt including the reason for such an action. The study will be suspended pending a further positive decision by the accredited Ethical Committee. The investigator will take care that all subjects are kept informed.

2. Adverse and serious adverse events, SUSARs

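### The plan promises to use drop-outs' data up to withdrawal, but the only method it names for repeated data would, in its classical form, discard those patients, and no other missing-data method is given

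*Combined protocol and SAP*

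**What the plan says.** Five places in the combined protocol and SAP bear on this.

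- **Statistical Analysis, drop-outs:** "Measurements of drop-outs will be included until the moment of withdrawal from the study".
- **Statistical Analysis, method:** "Repeated measurements ANOVA techniques will be used for analysis". The outcomes, model terms, covariance structure and handling of missing visits are not given. For the secondary parameters the section adds that, depending on the level of measurement, "a Chi-squared test or a T-test will be used to assess differences in secondary study parameters", with logistic and linear regression for baseline-corrected estimates.
- **Methods, 1.2 Primary endpoint:** "The primary endpoint is the mean eGFR decline which will be compared between the FO-group and the non-FO-group". The decline is each patient's regression slope of eGFR on time, and at least three eGFR "values are required to evaluate" it.
- **Methods, 4. Withdrawal of individual subjects:** "In case of withdrawal, an end of study visit will be scheduled to perform last measurements according to visit 5". After that, "Withdrawals will not be further followed".
- **Study Population, 4. Sample size calculation:** 86 patients per group are needed, and "In order to correct for drop-outs, at least 103 patients per group have to be included".

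Table 1 schedules eGFR at all six visits (months 0, 1, 3, 6, 9 and 12). Whole-body and thoracic bioimpedance (BIS) and blood pressure (BP) have no month 1 entry. The mixed clearance (CrUrCl) and the 24-hour urine have no visit 0 entry.

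**The concern.** Classical repeated-measures ANOVA works on one row per patient with every visit filled, and a patient with one empty cell is removed. The early measurements of a drop-out would then not enter, although the plan says they will. Two analysts could both follow the section, one with a complete-case ANOVA and one with a likelihood-based model, analyse different sets of patients, and both claim to have kept to the plan. The choice could be made after the data are seen.

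Selection is the main risk. The protocol lets the investigator withdraw a subject on pressing medical grounds, enrols stage 5 patients and records time to renal replacement therapy. It is plausible that those who leave differ in fluid status and decline from those who stay, although the documents give no figure for this. The secondary objective is longitudinal, and ANOVA is the only method named that is built for repeated values within a patient.

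The withdrawal visit adds a second problem. It is done to the visit 5 schedule, and in Table 1 the visit 5 column serves both month 12 and end of study. An analysis by visit slot would have to treat an early exit measurement as a month 12 value or discard it.

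**Working it through.** **1. The plan's own sample size.** Inputs from the sample size section: difference 2 per year, SD 4.7 per year, alpha 0.05 (taken as two-sided), power 0.80.

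n per group = 2 × [4.7 × (1.960 + 0.842) / 2]² = 86.7, or 87 rounded up. The stated 86 is reproduced to within one patient; its power is 0.797.

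Implied drop-out: 1 − 86/103 = 16.5%. The total is 2 × 103 = 206, of whom 2 × 86 = 172 are expected to complete.

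**2. Patients kept by a complete-case ANOVA.** Let m be the chance that a remaining patient misses any one follow-up visit, and k the number of follow-up visits at which the outcome is due. The documents give no value for m, so the range below is an assumption. So are independent misses, a visit 0 that is never missed, and a gap in every drop-out's record.

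Kept = 172 × (1 − m)^k

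| Assumed m | eGFR, six visits (k = 5) | BIS and BP, five visits (k = 4) |
|---|---|---|
| 0 | 172 | 172 |
| 2% | 172 × 0.904 = 155 | 172 × 0.922 = 159 |
| 5% | 172 × 0.774 = 133 | 172 × 0.815 = 140 |
| 10% | 172 × 0.590 = 102 | 172 × 0.656 = 113 |

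As shares of 206, the 5% row is 65% and 68%; the 10% row is 49% and 55%.

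**3. Patients kept by the primary slope rule.** Assume that the 206 − 172 = 34 drop-outs are spread evenly by last scheduled visit attended (visits 0 to 4), with no other misses.

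- Without the withdrawal visit, those who last attended visit 0 or 1 have fewer than three values: 34 × 2/5 = 13.6 lost, so about 192 of 206 are kept.
- With the withdrawal visit counted, only those who last attended visit 0 fall short: 34 × 1/5 = 6.8 lost, so about 199 are kept.

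Simulation with m = 10% added gives 191 and 198. The slope rule is therefore little affected by missed visits.

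**4. An analysis of all available data.** A linear mixed model uses whatever each patient has, so all 206 contribute to any outcome for which they have at least one value.

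**The case against.** The strongest defence is that the plan does not exclude anyone. It speaks of ANOVA techniques in general, fixes no model and states no deletion rule. Read together with the drop-out sentence, it can be taken to require a technique that accepts incomplete records, and a likelihood-based repeated-measures model would do so. This stands against the reading that the promise cannot be kept. It does not remove the need to name the method, because the classical form is an equally literal reading.

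Four other stronger readings are tempting, and the documents do not support them.

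- **The primary result shrinks to completers.** It does not. Section 1.2 defines a per-patient slope from at least three values, and the withdrawal visit can supply one of them.
- **Every secondary outcome is affected.** The plan also assigns t-tests, chi-squared tests and regression to the secondary parameters, and Table 1 schedules echocardiography and the SF36 only twice. The problem reaches only those outcomes that are in fact analysed across visits.
- **Power falls from 80% to about 69%.** That figure is what 133 patients would give for a difference of 2 with SD 4.7. Those inputs belong to the primary eGFR decline, and the fall needs the assumed 5% missed-visit rate. No secondary outcome has a planned effect size. The 16.5% loss alone leaves 86 per group, as planned.
- **Unequal visit spacing undermines the method throughout.** BIS and BP fall at months 0, 3, 6, 9 and 12, which is evenly spaced. Only outcomes with a month 1 measurement are unevenly spaced.

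**Conclusion.** The concern holds as a conflict between the inclusion rule and the classical form of the only repeated-data method named, with no missing-data rule to settle it. It is more than a missing detail, because a method that does what the plan intends is available at almost no cost.

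The size depends on what is lost. With the implied drop-out alone, the loss to a complete-case analysis is 34 of 206, which the sample size covers for power but not for selection. Anything beyond that rests on the assumed missed-visit rates. The direction and size of any selection bias cannot be worked out from the documents.

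**What to change.** In the Statistical Analysis section, replace the ANOVA sentence with wording to this effect: repeated outcomes will be analysed with a linear mixed model fitted by REML to all available measurements at their actual times, with group, time and group-by-time as fixed effects, and with patient random effects or a suitable within-patient covariance.

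Add three points:

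- The first measurement is part of the outcome vector and is not also a covariate. Table 1 gives the 24-hour urine and CrUrCl no visit 0 value to adjust for.
- The withdrawal visit is entered at its actual date, not as month 12.
- The model assumes that data are missing at random, given the measurements observed.

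The cost is a few sentences and standard software; no new data are needed. The downside is the missing-at-random assumption. Because patients are not followed after withdrawal, the study will hold no later data against which to check it, so it should be stated openly.
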